Any eligible participant is able to receive a COVID-19 test if they either (1) have COVID-19 symptoms; (2) have a known exposure to COVID-19; (3) need a test for travel, attending an event, or work-related requirement. Individuals are able to be tested repeatedly. Testing sites will occur regularly. There is no intervention being delivered in the testing component of the trial.

Interventions

The two interventions will be: (1) Short Message Service (SMS) with an associated link to a multi-media website and (2) Phone call with a peer.

In intervention 1, the participant will receive a SMS with a brief message containing the following: (1) statement encouraging them to get vaccinated, (2) the study's hotline number for a team member to assist in referring them for a vaccination, (3) a link to a multi-media page with videos and additional resources encouraging individuals to be vaccinated.

The multi-media website will be housed in the Safe Return To School website and updated by a designated study team members. This page will include the following COVID-19-related resources: publicly available vaccine promotion videos, videos consisting of community members discussing vaccine topics, resources regarding local vaccine sites, and links to additional literature resources.

In intervention 2, the participant's peer will be a study team member who has the same or similar racial demographic as the participant. All team members conducting the peer phone calls will be trained in motivational interviewing. The participant will be called by their peer via zoom or phone. Motivational interviewing techniques will be utilized with the participant to promote vaccine uptake. The team member will use a facilitator guide throughout the peer intervention.

D Study **Procedures**

D1 Testing

Recruitment and Consent

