The primary outcome of this study will be the percentage of individuals who received an initial vaccination within two weeks of a study intervention. Vaccine uptake will be primarily assessed by verbal confirmation of recent vaccination during a follow-up visit with a study team member. We will ask for visual documentation of the vaccine card or receipt that demonstrates the vaccine has been administered. Any participants lost to follow-up will be presumed "Unable to determine." A secondary outcome will be the number of individuals that complete their primary vaccination series within 6 weeks of their first dose.

In addition, data from the vaccine-uptake survey will analyzed for trends in willingness to vaccinate within participants. Changes promoting vaccine willingness could be indicative of an impactful vaccine intervention.

E Statistical Plan

Statistical considerations

Primary analysis

Our primary hypothesis is that the initial strategy of peer counseling will result in the highest vaccine uptake. To test this hypothesis we will use a generalized linear mixed model approach, assuming a binomial distribution and a logit link function. The intervention (peer counseling vs SMS + multimedia website) will be modeled as a fixed effect, and household will be included as a random effect to adjust for within household clustering. As this hypothesis focuses on addressing the best initial intervention, we will include only data collected through the first assessment in this analysis (~ 2 weeks following enrollment). If we find a significant difference (P < 0.05) and the proportion of vaccinated participants is greater in the peer counseling group, then we will conclude that the peer counseling is superior to the SMS + video as an initial vaccination strategy. We will also evaluate whether there is evidence of imbalance between the intervention groups for a variety of covariates including: age, race/ethnicity, sex, zip code, school district, highest education level, vaccine hesitancy, influenza vaccine history, previous COVID-19 illness, household member vaccinated, health insurance type, and perceived COVID-19 risk. If we find some evidence of a difference between the initial intervention groups (P <

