0.10) then those variables will be included in the final multivariable model to estimate the adjusted difference between the interventions. If we find no appreciable difference between the adjusted and unadjusted differences, then we will report the unadjusted difference as our primary result.

Secondary analyses

Our secondary analyses will entail analysis of non-responders as well as subgroup analyses. For those that do not respond to the initial intervention, we hypothesize that switching the intervention will result in the greatest vaccine uptake. We will use the same analytic strategy as in the analysis of the primary outcome, with the exceptions that: (1) we will only analyze participants that did not respond to the initial intervention (i.e., non-responders); and (2) we will test the null hypothesis of no difference in the proportion of participants agreeing to a vaccine between those non-responders that switched (peer \rightarrow SMS + multimedia website, SMS + multimedia website \rightarrow peer) compared to those that did not switch (peer \rightarrow Peer, SMS + multimedia website \rightarrow SMS + multimedia website).

For both the analysis of the initial intervention, and the non-responder analysis we will conduct several subgroup analyses. The subgroup analyses will entail analysis of vaccine uptake stratified by: age (<5, 5-11, 12-17, 18 and older), race (white vs black vs other), school district, health insurance, and gender identity. We will use the same analytical approach as previously discussed for the primary and secondary analyses. Results from these subgroup analyses will enable us to determine whether any of these groups modify the effect of vaccine uptake. Furthermore, estimates from these analyses (in addition to the primary analysis) are critical for understanding the factors that potentially modify vaccine uptake and applying results from our studies to other target populations with similar characteristics^{9,10}.

Sample size estimates

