We powered this study to test the primary hypothesis that an initial intervention of peer counseling will result in greater vaccine uptake compared to the SMS + multimedia website intervention. The sample size needed to test this hypothesis was based on pilot data as well as scientific literature on vaccination uptake. One research study estimated an increase COVID-19 vaccine uptake rate of 3.6% with a text reminder treatment compared to a holdout arm that did not receive a reminder^{11C}. Our listening session data from our community members, felt that receiving vaccination information from a peer would be helpful in becoming vaccinated. Additionally, peer counseling has been noted to increase breastfeeding rates in different race/ethnicity groups of at least 15%. For this reason, we estimate that 15% of participants will agree to a vaccine after having a conversation with a peer. Pilot data available for the study population indicated that the median household size was 1, and for the power analysis we assume 1 person per household but in the main analyses we will include a random effect to account for possible clustering at the household level if there is greater than one person per household. The aforementioned estimates from the literature served as our targets, but due to the inherent uncertainty in the application of results from prior studies to different target populations, we estimated the necessary sample sizes for a range of vaccine uptake-rates (Table 1). Based on these estimates we anticipate that a total drop-out adjusted sample size (peer counseling, SMS + multimedia website) ranging from 285 (increase in vaccine uptake of 12%) to 1113 (increase in vaccine update of 5%) would provide a minimum of 80% power to detect the

effect of interest. These sample sizes are attainable as we already have approximately 1000 unvaccinated individuals that we can contact for enrolment. Additionally, we will be adding more school districts to be eligible for testing. Lastly, we will recruit for enrollment beyond just testing as we utilize our community partners to help us with recruitment.

Increase in % uptake of vaccine	Total sample (unadjusted for drop out)	Total sample size + design effect*	Total sample (adjusted for 20% drop out)			
5%	712	890	1113			
7%	416	520	650			
9%	282	353	442			
12%	182	228	285			

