Table 1. Sample size estimates for different scenarios comparing the peer intervention to the SMS + multimedia website intervention. All scenarios assume 80% power and a 3.6% vaccine uptake rate for SMS + multimedia website based on results from Dai et al. 2021. *Design effect assumes an intracluster correlation of 0.50 and an average cluster size of 1.5.

Data management

All testing data are maintained in a secure, password-protected REDCap database. Information collected on paper forms is stored in locked filing cabinets on a restricted-access floor at WUSM. Prior to undergoing testing, participants will complete a HIPAA authorization form and/or informed consent to allow SARS-CoV-2 testing data to be shared with the State of Missouri. All participants are assigned an ID number, and testing information is kept separate from the demographic data. Subjects who test positive are contacted by phone to be given their results. This information will be shared only with the participant unless an informed consent is signed that will allow sharing of their data with the RADx-UP Coordination and Data Collection Center.. Data are stored using HIPAA-compliant encryption to comply with all local, state, and national regulations for health-related data.

Our existing Consortium Data Reporting Unit (CDRU), in collaboration with our data manager, will coordinate the submission of common data element metrics on SARS-CoV-2 testing-related outcomes to the RADx-UP CDCC at Duke University. We will comply with data sharing as mandated by the NIH and follow guidance provided by the CDCC for data acquisition, collection, and curation, including appropriate consent for data sharing and implementation of the schemas proposed under the ABOUT ML effort. The CDRU will also ensure compliance with federal, state, and local requirements and policies for testing, reporting, and surveillance. The CDRU will also work closely with the CDCC to employ a common set of tools to promote collection of comparable data on social determinants of health, including measures from the PhenX Toolkit. Effective implementation strategies for rapid adoption will be disseminated through the CDCC.

We will work collaboratively with the Duke CDCC in reviewing and revising our data collection tools to ensure we are collecting the appropriate CDEs. We will share our data with Duke

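### Peer calls are clustered by caller, but the primary model and the sample size allow only for household; if callers differ, the primary P value is too small and the power is overstated

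*Combined protocol and SAP*

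**What the plan says.** The Interventions part of section C describes intervention 2 as a motivational-interviewing conversation by phone or Zoom. The participant's "peer will be a study team member who has the same or similar racial demographic as the participant". There is more than one caller: "All team members conducting the peer phone calls will be trained in motivational interviewing". The calls are standardised to a degree: "The team member will use a facilitator guide throughout the peer intervention". The number of callers is not given, nor how one is chosen when several would match. The SMS arm receives a brief message and a link, with no assigned caller.

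The Primary analysis in section E is a logistic mixed model with intervention as a fixed effect; "household will be included as a random effect to adjust for within household clustering". No caller term appears, and caller is not among the covariates checked for imbalance. The decision rule reads "If we find a significant difference (P < 0.05) and the proportion of vaccinated participants is greater in the peer counseling group", in which case peer counselling is declared superior as an initial strategy.

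The sample size table carries one design effect, built from a household ICC of 0.50 and an average household of 1.5.

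Race (white, black, other) is a planned subgroup under Secondary analyses, where the plan says "Results from these subgroup analyses will enable us to determine whether any of these groups modify the effect of vaccine uptake".

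**The concern.** Everyone in the peer arm is nested within a caller, and nobody in the SMS arm is. If some callers persuade better than others, outcomes for the same caller are correlated and the peer-arm rate is less precise than a household-only model reports. The plan already accepts that clusters averaging 1.5 people need a random effect. Caller clusters could hold dozens of people or more than a hundred, and at that size even a small ICC matters.

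The planned conclusion concerns peer counselling as a strategy, so it reaches past the people who happen to make the calls. A significant result could rest on one or two effective callers. Matching on race also ties caller to participant race, so a race difference in the peer effect may be a difference between callers.

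**Working it through.** **Reproducing the plan's table.** Inputs from the Sample size estimates section: "All scenarios assume 80% power and a 3.6% vaccine uptake rate for SMS + multimedia website". Two-sided 5% and 1:1 allocation are not stated, but they reproduce the table. Per arm, n = (1.96 + 0.8416)² × [p₁(1−p₁) + p₂(1−p₂)] / d².

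- For +5 points: 7.849 × (0.0347 + 0.0786) / 0.0025 = 355.7, so 356 per arm and 712 in total.
- Design effect: 1 + (1.5 − 1) × 0.50 = 1.25, and 712 × 1.25 = 890.
- Dropout: 890 / 0.80 = 1112.5, printed as 1113.
- The other rows also match (416, 282 and 182 before adjustment). The 1.25 is used up by household, which leaves nothing for caller.

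**Analysed per arm.** 1113 × 0.80 ≈ 890, or 445 per arm. 285 × 0.80 = 228, or 114 per arm.

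**Assumptions not in the documents.** Callers: 4, with 20 as a contrast. Caller ICC: 0.01, 0.02, 0.05.

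**Type I error.** With m analysed peer-arm participants per caller, the variance factor is 1.25 + (m − 1) × ICC in the peer arm and 1.25 in the SMS arm. With equal average rates, the true variance of the difference exceeds the modelled variance by

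R = [2.5 + (m − 1) × ICC] / 2.5,

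and the type I error is 2 × [1 − Φ(1.96/√R)].

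Example with 4 callers, 445 per arm and ICC 0.02: m = 111.25; 110.25 × 0.02 = 2.205; R = 4.705/2.5 = 1.882; 1.96/√1.882 = 1.429; type I error 15.3%.

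| Callers | Per arm | m | ICC 0.01 | ICC 0.02 | ICC 0.05 |
|---|---|---|---|---|---|
| 4 | 114 | 28.5 | 6.3% | 7.6% | 11.5% |
| 4 | 445 | 111.25 | 10.3% | 15.3% | 27.4% |
| 20 | 114 | 5.7 | 5.2% | 5.4% | 6.1% |
| 20 | 445 | 22.25 | 6.0% | 7.0% | 10.1% |

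At ICC 0 every entry is 5%. Because superiority also requires higher uptake in the peer group, false claims for peer counselling are about half of each entry, against a nominal 2.5%.

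**Simulation check.** A beta-binomial simulation (20,000 runs per cell, one person per household) with 5 callers, 445 per arm and ICC 0.02 gave about 15%. It has no household clustering, so the matching formula value uses 1 in place of 1.25: R = (2 + 88 × 0.02)/2 = 1.88, giving 15.3%. With 1.25 the value is 13.3%.

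**Power of a test that allows for caller, +5 points, 445 per arm.** V = [0.0347 × 1.25 + 0.0786 × (1.25 + (m − 1) × ICC)] / 445 and power = Φ(0.05/√V − 1.96).

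- ICC 0: V = 0.000318, power 0.80.
- 4 callers, ICC 0.01: V = 0.000513, power 0.60.
- 4 callers, ICC 0.02: V = 0.000708, power 0.47.
- 5 callers: 0.63 and 0.51 by the same formula, or about 0.66 and 0.57 with a pooled null variance.

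These are normal approximations that add the household and caller terms. With few callers, small-sample degrees of freedom would lower power further.

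**The case against.** The strongest reply is that none of this is shown to occur. It needs callers who differ and callers who are few, and the documents establish neither. Common training and a guide used throughout the call make a small ICC more plausible. With 20 callers and 114 per arm the error is 5 to 6%, which is negligible. This stands: the result is conditional.

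The null also needs care. If calls affect nobody, callers cannot differ in persuasiveness and the test keeps its level. It also keeps its level if inference is confined to the callers used. The figures above describe a zero average effect over a population of callers. At 3.6% uptake, ICC 0.05 implies a between-caller SD of √(0.05 × 0.036 × 0.964) = 4.2 points, larger than the mean; ICC 0.02 implies 2.6 points. The upper figures are therefore an outer range. Restricting inference to these callers, however, does not fit a conclusion about a strategy.

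A caller variance may also be poorly estimated. In the 285 scenario the plan implies about 114 × 0.036 = 4 SMS events and 114 × 0.156 = 18 peer events. That is too thin for a caller effect in the only primary model, and it argues for a sensitivity analysis instead.

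A reader might infer that callers are allocated non-randomly and that this causes the problem. The documents are silent on the choice among race-matched callers, and randomly assigned callers would still cluster the peer arm. Race matching is part of the intervention and leaves the randomised comparison unbiased.

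**Conclusion.** The point holds conditionally. The plan sets caller variance to zero, without saying so, in both the analysis and the sample size. If that variance is above zero, the primary P value is too small and the power overstated for a claim about peer counselling beyond these callers. The size depends on two assumed inputs: it is modest to large with about 4 callers, small with about 20 callers at the lower sample size, and zero at ICC 0.

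A reader might conclude that the P value is simply wrong, or might leave out the household factor and quote larger errors. The documents support neither: they give no caller ICC, and the plan's own 1.25 belongs in the calculation.

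The race-subgroup point is a limit on interpretation of a secondary analysis and does not touch the primary test. The tabulated errors also do not carry over to the second-stage comparison of switching with staying, because peer calls occur on both sides of it.

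**What to change.** - State the planned number of callers and record caller ID for every peer call at both stages, for example in the tracking log already in the project timeline.
- Where more than one race-matched caller is available, assign by rotation or at random.
- Prespecify a sensitivity analysis of the primary comparison with a caller random effect for peer-arm participants only (a partially nested model), alongside household, with small-sample degrees of freedom.
- Report peer-arm uptake by caller.
- For the second stage, attach the caller term to whoever received a stage-2 peer call, whether by switching from SMS or by repeating the peer call.
- State that race-subgroup differences in the peer effect cannot be separated from caller.

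The cost is one data field, a caller rota and one additional model, with no extra staff or participants. The interval in the sensitivity analysis will be somewhat wider, and the caller variance will be imprecise if callers are few. Caller ID should be captured at the call, since it may not be recoverable later.

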Once enrolled into the study, each participant will be initially randomized into one of the two intervention groups: (1) SMS + multi-media page, or (2) Phone call with a peer. For household members, randomization will occur at the family unit and all participants will receive the same intervention. All participants will be asked at the start of the study a vaccine-uptake survey regarding the following: their overall willingness to get vaccinated and willingness to vaccinate their children (if applicable); factors that increase and decrease willingness to vaccinate, and their barriers that inhibited their ability to vaccinate.

Within one week of enrollment, the participant/family unit will receive the first intervention. A study team member will follow-up with the participant(s) to determine any changes in vaccination status at the two-weeks receiving their first intervention. If the participant(s) have no changes in their vaccination status, the participant/family unit will undergo a second round of randomization within one week of this follow-up. The same two interventions will be used, so an

individual will receive *either* a second exposure to the same intervention or the intervention that they did not initially receive. After two weeks of the participant's 2nd randomization, a study team member will follow-up a second time to determine vaccination status. During each follow-up session, a study team will provide the same vaccine-uptake survey to the participant and offer to provide vaccine resources on where to obtain a vaccine for the participants. If a participant receives a vaccine an additional phone call will be performed 4 weeks after their first vaccine dose to assess if they completed the primary vaccination series. Compensation of \$100 will be provided for those individuals consenting to this study. This compensation will be provided in allotments of \$50 after completing the consent document and then \$25 after each randomization. If a participant does not need to be randomized a second time, the second \$25 will be provided when learning of the participant receiving their vaccine.

Assessing Vaccine Strategies

The primary outcome of this study will be the percentage of individuals who received an initial vaccination within two weeks of a study intervention. Vaccine uptake will be primarily assessed by verbal confirmation of recent vaccination during a follow-up visit with a study team member. We will ask for visual documentation of the vaccine card or receipt that demonstrates the vaccine has been administered. Any participants lost to follow-up will be presumed "Unable to determine." A secondary outcome will be the number of individuals that complete their primary vaccination series within 6 weeks of their first dose.

In addition, data from the vaccine-uptake survey will analyzed for trends in willingness to vaccinate within participants. Changes promoting vaccine willingness could be indicative of an impactful vaccine intervention.

E Statistical Plan

Statistical considerations

Primary analysis

Our primary hypothesis is that the initial strategy of peer counseling will result in the highest vaccine uptake. To test this hypothesis we will use a generalized linear mixed model approach, assuming a binomial distribution and a logit link function. The intervention (peer counseling vs SMS + multimedia website) will be modeled as a fixed effect, and household will be included as a random effect to adjust for within household clustering. As this hypothesis focuses on addressing the best initial intervention, we will include only data collected through the first assessment in this analysis (~ 2 weeks following enrollment). If we find a significant difference (P < 0.05) and the proportion of vaccinated participants is greater in the peer counseling group, then we will conclude that the peer counseling is superior to the SMS + video as an initial vaccination strategy. We will also evaluate whether there is evidence of imbalance between the intervention groups for a variety of covariates including: age, race/ethnicity, sex, zip code, school district, highest education level, vaccine hesitancy, influenza vaccine history, previous COVID-19 illness, household member vaccinated, health insurance type, and perceived COVID-19 risk. If we find some evidence of a difference between the initial intervention groups (P <

0.10) then those variables will be included in the final multivariable model to estimate the adjusted difference between the interventions. If we find no appreciable difference between the adjusted and unadjusted differences, then we will report the unadjusted difference as our primary result.

Secondary analyses

Our secondary analyses will entail analysis of non-responders as well as subgroup analyses. For those that do not respond to the initial intervention, we hypothesize that switching the intervention will result in the greatest vaccine uptake. We will use the same analytic strategy as in the analysis of the primary outcome, with the exceptions that: (1) we will only analyze participants that did not respond to the initial intervention (i.e., non-responders); and (2) we will test the null hypothesis of no difference in the proportion of participants agreeing to a vaccine between those non-responders that switched (peer \rightarrow SMS + multimedia website, SMS + multimedia website \rightarrow peer) compared to those that did not switch (peer \rightarrow Peer, SMS + multimedia website \rightarrow SMS + multimedia website).

For both the analysis of the initial intervention, and the non-responder analysis we will conduct several subgroup analyses. The subgroup analyses will entail analysis of vaccine uptake stratified by: age (<5, 5-11, 12-17, 18 and older), race (white vs black vs other), school district, health insurance, and gender identity. We will use the same analytical approach as previously discussed for the primary and secondary analyses. Results from these subgroup analyses will enable us to determine whether any of these groups modify the effect of vaccine uptake. Furthermore, estimates from these analyses (in addition to the primary analysis) are critical for understanding the factors that potentially modify vaccine uptake and applying results from our studies to other target populations with similar characteristics^{9,10}.

Sample size estimates

We powered this study to test the primary hypothesis that an initial intervention of peer counseling will result in greater vaccine uptake compared to the SMS + multimedia website intervention. The sample size needed to test this hypothesis was based on pilot data as well as scientific literature on vaccination uptake. One research study estimated an increase COVID-19 vaccine uptake rate of 3.6% with a text reminder treatment compared to a holdout arm that did not receive a reminder^{11C}. Our listening session data from our community members, felt that receiving vaccination information from a peer would be helpful in becoming vaccinated. Additionally, peer counseling has been noted to increase breastfeeding rates in different race/ethnicity groups of at least 15%. For this reason, we estimate that 15% of participants will agree to a vaccine after having a conversation with a peer. Pilot data available for the study population indicated that the median household size was 1, and for the power analysis we assume 1 person per household but in the main analyses we will include a random effect to account for possible clustering at the household level if there is greater than one person per household. The aforementioned estimates from the literature served as our targets, but due to the inherent uncertainty in the application of results from prior studies to different target populations, we estimated the necessary sample sizes for a range of vaccine uptake-rates (Table 1). Based on these estimates we anticipate that a total drop-out adjusted sample size (peer counseling, SMS + multimedia website) ranging from 285 (increase in vaccine uptake of 12%) to 1113 (increase in vaccine update of 5%) would provide a minimum of 80% power to detect the

effect of interest. These sample sizes are attainable as we already have approximately 1000 unvaccinated individuals that we can contact for enrolment. Additionally, we will be adding more school districts to be eligible for testing. Lastly, we will recruit for enrollment beyond just testing as we utilize our community partners to help us with recruitment.

Increase in % uptake of vaccine	Total sample (unadjusted for drop out)	Total sample size + design effect*	Total sample (adjusted for 20% drop out)			
5%	712	890	1113			
7%	416	520	650			
9%	282	353	442			
12%	182	228	285			

Table 1. Sample size estimates for different scenarios comparing the peer intervention to the SMS + multimedia website intervention. All scenarios assume 80% power and a 3.6% vaccine uptake rate for SMS + multimedia website based on results from Dai et al. 2021. *Design effect assumes an intracluster correlation of 0.50 and an average cluster size of 1.5.

Data management

All testing data are maintained in a secure, password-protected REDCap database. Information collected on paper forms is stored in locked filing cabinets on a restricted-access floor at WUSM. Prior to undergoing testing, participants will complete a HIPAA authorization form and/or informed consent to allow SARS-CoV-2 testing data to be shared with the State of Missouri. All participants are assigned an ID number, and testing information is kept separate from the demographic data. Subjects who test positive are contacted by phone to be given their results. This information will be shared only with the participant unless an informed consent is signed that will allow sharing of their data with the RADx-UP Coordination and Data Collection Center.. Data are stored using HIPAA-compliant encryption to comply with all local, state, and national regulations for health-related data.

Our existing Consortium Data Reporting Unit (CDRU), in collaboration with our data manager, will coordinate the submission of common data element metrics on SARS-CoV-2 testing-related outcomes to the RADx-UP CDCC at Duke University. We will comply with data sharing as mandated by the NIH and follow guidance provided by the CDCC for data acquisition, collection, and curation, including appropriate consent for data sharing and implementation of the schemas proposed under the ABOUT ML effort. The CDRU will also ensure compliance with federal, state, and local requirements and policies for testing, reporting, and surveillance. The CDRU will also work closely with the CDCC to employ a common set of tools to promote collection of comparable data on social determinants of health, including measures from the PhenX Toolkit. Effective implementation strategies for rapid adoption will be disseminated through the CDCC.

We will work collaboratively with the Duke CDCC in reviewing and revising our data collection tools to ensure we are collecting the appropriate CDEs. We will share our data with Duke

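### The second follow-up is timed from the second randomisation, not from the second intervention, so the two-week outcome window at stage 2 can be cut short

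*Combined protocol and SAP*

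**What the plan says.** Section D2, Assessing Vaccine Strategies, defines the primary outcome as the "percentage of individuals who received an initial vaccination within two weeks of a study intervention". The clock in that definition starts at an intervention.

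Section D2, Randomization, sets the visit schedule:

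- **First delivery:** "Within one week of enrollment, the participant/family unit will receive the first intervention".
- **First follow-up:** to "determine any changes in vaccination status at the two-weeks receiving their first intervention".
- **Second randomisation:** those with no change in status "will undergo a second round of randomization within one week of this follow-up".
- **Second delivery:** no time limit is given.
- **Second follow-up:** "After two weeks of the participant's 2nd randomization, a study team member will follow-up a second time to determine vaccination status".
- **Later contact:** a call four weeks after the first dose, only for participants who have received a vaccine.

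Section E, Secondary analyses, compares non-responders who switched intervention with those who repeated it. It says "We will use the same analytic strategy as in the analysis of the primary outcome", with stated exceptions, and words the outcome as agreement to a vaccine rather than receipt of one.

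Section E, Primary analysis, gives a further clock for the first assessment: "we will include only data collected through the first assessment in this analysis (~ 2 weeks following enrollment").

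**The concern.** The endpoint and the first follow-up start their two weeks at the intervention. The second follow-up starts its two weeks at the second randomisation. Any day that passes before the second text or call is delivered comes off the observed window. A vaccination on day 10 after a call made on day 6 falls on day 16 after randomisation. It meets the outcome definition but comes after the only scheduled stage-2 outcome visit.

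Some lag is plausible. The protocol allows up to a week to deliver the first intervention. A peer call needs a team member trained in motivational interviewing whose racial demographic matches or resembles the participant's (section C, Interventions), and it has to be arranged. At stake is the non-responder analysis with its subgroups, which is the only planned use of the second randomisation.

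**Working it through.** **1. The plan's own figures.** The sample-size table covers stage 1 only. With unpooled variance, two-sided 5% alpha, 80% power and 1:1 allocation, n per arm = (1.960 + 0.842)² × [p₀(1−p₀) + p₁(1−p₁)] / (p₁−p₀)².

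- 3.6% vs 8.6%: 7.849 × (0.0347 + 0.0786) / 0.0025 = 355.7, so 356 per arm and 712 in total.
- 3.6% vs 15.6%: 7.849 × (0.0347 + 0.1317) / 0.0144 = 90.7, so 91 per arm and 182 in total.

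Both match the table. The design effect 1 + 0.5 × 0.50 = 1.25 and division by 0.80 give 890 and 1113 for the first row. None of this depends on the second follow-up. The plan states no stage-2 effect, sample size or power.

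**2. The clocks side by side.**

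| | Clock starts at | Delivery limit |
|---|---|---|
| Outcome definition | an intervention | – |
| First follow-up (D2) | receipt of first intervention | 1 week from enrolment |
| First assessment (E) | enrolment | – |
| Second follow-up (D2) | second randomisation | none stated |

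**3. Window observed at stage 2.** Let L be the days from second randomisation to second delivery. L is not in the documents; 0 to 7 days is assumed, matching the stage-1 limit. With follow-up on day 14, the observed fraction is (14 − L)/14:

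- L = 0: 100%
- L = 2: 12/14 = 86% (14% lost)
- L = 3.5: 10.5/14 = 75%
- L = 7: 7/14 = 50%

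**4. What that does to recorded uptake.** Under a constant hazard, a 14-day rate p is recorded as 1 − (1 − p)^((14−L)/14). The rates below come from the sample-size table and serve only as illustrations of stage-2 uptake.

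| 14-day rate | L = 0 | L = 2 | L = 3.5 | L = 7 |
|---|---|---|---|---|
| 3.6% | 3.6% | 3.1% | 2.7% | 1.8% |
| 8.6% | 8.6% | 7.4% | 6.5% | 4.4% |
| 15.6% | 15.6% | 13.5% | 11.9% | 8.1% |

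For example, at L = 7, 1 − 0.844^0.5 = 8.1%. With lags spread evenly over 0 to 7 days, 15.6% becomes about 11.9%.

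**5. Can a power loss be attached?** Only with a stage-2 effect, and the answer depends on which one is assumed. Take 182 evaluable participants. Non-responders are 91 × 0.964 + 91 × 0.844 = 87.7 + 76.8, about 165.

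- If repeat is 3.6% and switch 15.6%, power (two-sided z-test, clustering ignored) is 75% at no lag and 46% at 7 days.
- If the same rates follow the intervention received at stage 2, switch is (76.8 × 3.6% + 87.7 × 15.6%)/164.5 = 10.0% and repeat is (76.8 × 15.6% + 87.7 × 3.6%)/164.5 = 9.2%. Power is then about 5% at any lag.

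The table's rates are for peer versus SMS, whereas switch and repeat each mix both. The documents do not choose between these cases.

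**6. First-assessment wording.** Delivery up to 7 days after enrolment plus 14 days puts the first follow-up as late as day 21 after enrolment, whereas section E says about two weeks.

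**The case against.** The strongest reply is that nothing need be lost. No stage-2 lag is documented, same-day delivery leaves the full window, and the two-week interval before the second follow-up could be read as a minimum. All of this stands, and it makes the loss conditional. It does not remove the need for repair: with no delivery limit the full window is not guaranteed, and a minimum with no upper bound gives follow-up no fixed time.

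Three stronger readings are tempting, and the documents do not support them:

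- **That the switch-versus-repeat test loses a known amount of power.** A reader might carry the sample-size rates into stage 2 and infer a fall such as 75% to 46%. Those rates describe another contrast, and the plan gives the stage-2 test no effect or power from which to measure a loss.
- **That slower delivery of calls biases the stage-2 comparison.** Calls may well take longer than texts, but switch and repeat each contain both, so the difference would largely balance in the pooled contrast. The plan specifies no comparison of the four sequence-specific rates.
- **That stage 2 is the only place where the clocks disagree.** The first assessment also has two anchors, receipt of the intervention in D2 and enrolment in E. That is a separate inconsistency to reconcile; it is not a consequence of the second follow-up rule.

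It is also fair to say that the stage-2 outcome is loosely defined, since it is worded as agreement to a vaccine. The shared analytic strategy may mean only the model. That argues for defining the outcome.

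**Conclusion.** The mismatch is in the text. The outcome and the first follow-up in D2 run from the intervention, the second follow-up runs from the second randomisation, second delivery has no limit, and no later contact would pick up people still unvaccinated. Qualifying stage-2 vaccinations can therefore be missed, and recorded uptake among non-responders lowered.

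The size depends on the lag: none with same-day delivery, about 14% of the window at 2 days, half at 7 days. This assumes follow-up on day 14, a constant vaccination hazard, and a lag of 0 to 7 days that the documents do not give. The effect is confined to a secondary analysis; the second follow-up rule does not touch the stage-1 primary analysis. It is worth correcting because the repair is cheap.

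**What to change.** - **D2, Randomization:** state that the second intervention is delivered within one week of the second randomisation. Hold the second follow-up three weeks after the second randomisation for everyone, in all four sequences. Record the dates of delivery and vaccination.
- **E, Secondary analyses:** define the stage-2 outcome as receipt of a first vaccination, not agreement to one, by day 21 from the second randomisation. Derive vaccination within 14 days of delivery, the D2 outcome, from the recorded dates. Delivery by day 7 plus 14 days ends on day 21, so one visit serves both.
- **E, Primary analysis:** reconcile the enrolment-based timing of the first assessment with the first follow-up in D2.

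A common day matters. If follow-up were instead set 14 days after each person's delivery, someone reached on day 0 would be seen on day 14 and their status at day 21 would be unknown.

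Cost: protocol and SAP wording, and second follow-up calls up to one week later. No extra contacts, staff or participants.
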